2.5 Other Factors

Viral Load, SARS-CoV-2 Serology, Pharmacokinetic drug concentration, patient demographics and clinical severity (baseline OSCI score) will be included in the pathway analysis model. These factors will be coded as numerical values and input as clinical traits for analysis of correlation with eigengene values of gene cluster modules within the WGCNA work stream.

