1.1 Study Population

The inclusion criteria for the ACCORD trial were:

Adults (>= 18 years) with SARS-CoV-2 infection confirmed by laboratory tests and/or point of care tests. Patients must be scored between Grade 3 (hospitalised – mild disease, no oxygen therapy) to Grade 5 (hospitalised - severe disease, non-invasive ventilation or high flow oxygen) on ACCORD's 9 point WHO ordinal scale from clinical improvement (OSCI) where Grade 0 is uninfected and 8 is death. Overall, in the ACCORD study 167 subjects were randomised, 14 subjects withdrew and 25 subjects died. In the additional Bemcentinib study, a further 115 were randomised – 60 to SoC and 55 to Bemcentinib in an identical study design.

1.2 Sampling.

Samples from patients were collected in line with the sample collection schedule below:

	Baseline								
Day	1	3	4	5	8	10	11	15	29
Biological sample type									
Blood (for RNA)	Х			Х		Х			
Blood (for serology)	Х							Х	
Blood (for protein)	Х			Х		Х			
Oropharyngeal swab (for viral load)	Х	Х		Х	Х		Х	Х	Х
Pharmacokinetic drug concentration									
Bemcentinib	Х		Xa		Х			Х	
Tozorakimab	Xb							Xc	
Zilucoplan	Х			Х		Х		Х	

Table showing the sample collection schedule for the ACCORD COVID-19 clinical trial.

Adapted from (1) to show only the samples collected to generate the datasets relevant to this current project. X = sample collected. All patients were sampled on day 1, which is considered baseline prior to the first dose of the assigned treatment arm or standard of care. Each drug had slightly different pharmacokinetic (PK) sampling regimes and were mostly collected predose. Where samples for PK were collected other than pre-dose, collection information is detailed below:

- ^a Sample collected pre-dose and 6 hours post-dose (Day 4).
- ^b Sample collected pre-dose and 15 minutes post-dose (Day 1).
- ^c Sample collected pre-dose and 15 minutes post-dose (Day 15).

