1.2.1 Datasets

The datasets generated from the above sampling protocol of the ACCORD trial include transcriptomics, proteomics, viral load, serology, pharmacokinetic drug concentration and clinical laboratory datasets. Further information about the generation and processing of each dataset is outlined below:

1.2.1.1 Transcriptomic dataset (RNA Sequencing)

Sequencing was performed on patient blood samples taken on days 1 (at baseline prior to treatment), day 5 and day 10 of admission to hospital. A total of 286 samples were sequenced using an Illumina NovaSeq 600 platform. Total RNA was prepared from blood and depleted of highly abundant transcripts for alpha and beta haemoglobin and ribosomal RNA. No more than 50 samples per 'lane' were multiplexed to maximise sequence read depth to ensure a minimum sample read depth of 100 to 150 M. Quality control (QC) of raw read data was performed using FastQC version 0.11.9 and compiled and visualised using MultiQC version 1.12. Samples with <20 million total reads and less than 50% of the total read count were excluded from further analysis. After MultiQC analysis, fourteen sample were removed that failed quality control, leaving 272 high-quality samples available in the transcriptomic dataset for downstream analysis.

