2.2 Comparison and confounding of baseline clinical characteristics

Baseline clinical characteristics, including age, sex, ethnicity, significant comorbidities, laboratory results and clinical observations will be recorded, assessed and compared between patients in different treatment arms using R (v 4.1.2). Patient statistics tables will be calculated to test for any significant confounding variables between blinded groups. Principal component analysis of normalised expression values will be correlated with axes of variation e.g. ethnicity, to identify clusters affecting gene expression.

Differential gene expression analysis will control for baseline factors that may skew analysis by updating the statistic model design in DESeq2. Differential splicing analysis will be subject to weighting by multinomial covariate-balanced propensity scores to control for baseline confounding factors, as implemented by the R package Weightlt version 0.12.0, using the "just-identified" approach. Proteomics models will incorporate weighted baseline clinical data to avoid bias.

2.3 Transcriptomic analysis

The focus of this study will be the analysis of the transcriptomics dataset comprising patient data taken at three time points for three novel drugs and the SoC trial arm. The RNA-Sequencing samples have been generated and the raw FASTQC data have been downloaded from the ACCORD clinical trials platform. These data have been subject to quality control as previously described in the methods section. To avoid any unintentional bias, the groups will be blinded so that the bioinformatician will not know which patient group or SoC arm is which. The novel drug and SoC arms will be given a random identifier such as A, B, C or D for the duration of this analysis.

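### Section 2.2 does not name Day 1 viral load or Day 1 serostatus among the baseline factors for the gene, splicing and protein contrasts, and the expected protein test cannot adjust for them

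*Protocol*

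**What the plan says.** **Who is in the data.** Protocol section 1.1 restates the parent trial's inclusion criteria: adults "with SARS-CoV-2 infection confirmed by laboratory tests and/or point of care tests", in OSCI Grades 3 to 5. No window since symptom onset or positive test appears in that restatement.

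**What is measured at baseline.** Section 1.2 states: "All patients were sampled on day 1, which is considered baseline prior to the first dose of the assigned treatment arm or standard of care". Its schedule puts both the viral-load swab and the serology sample on Day 1. Swabs are repeated on Days 3, 5, 8, 11, 15 and 29, and serology on Day 15.

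**Where viral load and serology are used.** Section 2.5 says that "Viral Load, SARS-CoV-2 Serology, Pharmacokinetic drug concentration, patient demographics and clinical severity (baseline OSCI score") "will be included in the pathway analysis model", and then describes them as traits to be correlated with WGCNA module eigengenes. Viral load also enters the machine-learning integration (2.6) and is a stratifier in the outlier analysis (2.6.3).

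**What the contrasts adjust for.** Section 2.2 compares baseline characteristics "including age, sex, ethnicity, significant comorbidities, laboratory results and clinical observations". It promises control for baseline factors through the DESeq2 design, through propensity-score weights for splicing, and through weighted baseline data for proteins. It does not say which factors these are.

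**The protein test.** Section 2.4 expects Mann-Whitney tests, both for each drug against SoC and for responders against non-responders within each drug arm.

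**The concern.** On Day 1 a hospitalised patient may be early in infection (high viral load, antibody negative) or late (low viral load, antibody positive). Interferon, B-cell and cytokine signals can be expected to depend on that phase, and these are among the readouts from which the project will infer drug mechanism. The two scheduled measurements that best indicate phase are assigned by name to pathway, WGCNA and machine-learning work, and not to the models behind the gene, splicing and protein contrasts.

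The consequence depends on the contrast:

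- **Drug versus SoC** (randomised): unexplained variance, and a result that may reflect a chance difference in phase between small arms.
- **Responder versus non-responder** (not randomised): phase may be related to both recovery and expression, so it can confound directly.

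Section 2.5 ties only the OSCI score to baseline. A post-treatment viral load or Day 15 serology could therefore be used as an adjuster unless the plan excludes it.

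**Working it through.** The protocol gives no power or sample-size figure for these contrasts, so there is none to reproduce. The check traces the text and then sizes the effect under stated assumptions.

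**1. Does the baseline list in 2.2 already cover these measures?** The list is open-ended and includes laboratory results. However, the protocol treats viral load (1.2.1.3) and serology (1.2.1.4) as separate datasets, and describes the clinical laboratory dataset (1.2.1.6) as haematology, coagulation and clinical chemistry. The natural reading is that 2.2 does not name them, though it does not exclude them.

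**2. Can each planned method carry them?**

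| Contrast | Method | Can it adjust? |
|---|---|---|
| Genes | DESeq2 design (2.2, 2.3.1) | Yes, if named |
| Pathway scores | limma (2.3.3) | Yes; 2.5 mentions a pathway model but not which day's value |
| Splicing | Propensity weights (2.2) | Yes, if named |
| Proteins | Mann-Whitney (2.4) | No; this also sits poorly with the weighted protein models in 2.2 |

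**3. Patients per arm.** Section 1.2.1.1 gives 286 − 14 = 272 samples. Over three time points and four arms, 272 / (3 × 4) = 22.7, so about 23. This assumes equal arms and complete series; the protocol gives no arm sizes for this dataset.

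**4. Precision.** Assume phase explains a share R² of a marker's variance. The relative sample size needed without adjustment is 1/(1 − R²):

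- R² = 0.10: 1/0.90 = 1.11, or 11% more patients.
- R² = 0.30: 1/0.70 = 1.43, or 43% more patients.

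As power, for an assumed difference of 0.8 SD at 23 per arm (two-sided 0.05, one test):

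| R² | Power |
|---|---|
| 0 (unadjusted) | 77% |
| 0.10 | 82% |
| 0.30 | 90% |

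Multiplicity correction will lower all of these.

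**5. Chance imbalance.** Assume a share p of patients is late-phase. The SD of the between-arm difference is √(2p(1 − p)/n). At n = 23 and p = 0.5 this is √(2 × 0.25/23) = 0.147, or about 15 points. Exact two-binomial probability of a difference of 20 points or more:

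| n per arm | p = 0.3 | p = 0.5 |
|---|---|---|
| 15 | 32% | 36% |
| 23 | 15% | 18% |
| 55 | 3% | 4–5% |

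**6. Would the baseline tables in 2.2 catch it?** Section 2.2 looks for significant confounders. At 23 per arm, when the arms do differ by 20 points or more, Fisher's exact test at 0.05 flags about 17% of cases for p = 0.3 and 14% for p = 0.5. Screening by significance would miss most such imbalances.

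**The case against.** **Baseline adjustment is already promised, and the covariate list could sit in an SAP.** It is true that 2.2 covers all three contrast types with an open list, and silence alone would not be a finding. But the protocol carries its own analysis plan, detailed down to software versions and the type of propensity weighting. It names these two measures and places them elsewhere, and it expects a protein test that cannot adjust. The point stands as an allocation to correct, not as adjustment ruled out.

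**A reader might infer that the markers serve only as WGCNA traits.** The text does not support this. Section 2.5 also refers to the pathway analysis model, and viral load is used in 2.6 and 2.6.3. None of these uses clearly adjusts the gene, splicing or protein contrasts.

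**A reader might infer that the trial enrolled without any time limit, or included patients infected in hospital.** Section 1.1 is a brief restatement of a parent trial's inclusion criteria and gives no exclusion criteria. The absence of a window holds only for what is listed here, and the point does not need it.

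**A reader might infer that drug-versus-SoC results are biased.** Those arms are randomised, so the cost is precision and chance imbalance. The objection that these are largely one cost also stands: an unadjusted standard error already allows for random imbalance, so steps 4 and 5 should not be added together.

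**Limits of the remedy.** A Day 1 main effect does not separate drug effect from natural course in the pre/post contrasts. Nucleoprotein IgG may reflect an earlier infection, so serostatus is an imperfect marker of phase.

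**Conclusion.** The point holds in a limited form and is worth acting on. Section 2.2 leaves its adjustment factors unnamed and does not mention Day 1 viral load or serostatus; section 2.5 assigns them to other work; section 2.4 expects a test that cannot use them. Drug-versus-SoC contrasts lose precision, by the equivalent of 11% to 43% more patients for phase-related markers, and remain open to a 20-point phase imbalance in roughly one comparison in six. Responder contrasts may be confounded, by an amount that the documents do not allow one to size.

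These figures rest on assumptions: a variance share of 10% to 30%, a late-phase share of 30% to 50%, and about 23 patients per arm. The text findings need none of them. The documents do not show that adjustment for phase is excluded, or that every contrast mixes early and late disease unadjusted.

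**What to change.** 1. **Section 2.2.** Pre-specify Day 1 serostatus (positive/negative) and Day 1 log viral load (undetectable set at the assay limit) as covariates in the DESeq2, limma and splicing-weight models for the drug-versus-SoC contrasts. Use Day 1 values only, since later values may be affected by treatment. Report responder contrasts with and without them.
2. **Section 2.4.** Replace the Mann-Whitney test with a model that can carry covariates, for example a linear model on log or rank-transformed concentration that includes the Day 1 protein value.
3. **Section 2.5.** Keep both measures as WGCNA traits.
4. **Separate wording point.** Sections 1.2.1.1 and 1.2.1.2 count sampling days from admission (1.2.1.1: "days 1 (at baseline prior to treatment), day 5 and day 10 of admission to hospital"), while 1.2 defines Day 1 as baseline before first dose. These differ for anyone enrolled after the day of admission and should be reconciled.

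**Cost.** Both measures are on the Day 1 schedule, so no new sampling is needed. The price is about two degrees of freedom per model, a possible small loss of effective sample size in the splicing weights, and a stated rule for any missing Day 1 swab or serum.

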2.3.2 Weighted Gene Correlation Network Analysis (WGCNA)

The normalized dataset will undergo variance stabilizing transformation (vst) using the DESeq2 package, to be further explored using Weighted Gene Correlation Network Analysis (WGCNA)(4). WGCNA is an unsupervised analysis method which clusters genes into defined modules of highly interconnected genes based on the similarity of gene co-expression profiles. These modules can be assessed for correlations with specific clinical traits; specifically, we will assess whether any gene module is associated with one of the blinded treatment arms. Additionally, for each gene module, 'hub' genes can be identified, which are genes with high connectivity, and therefore high importance, within a co-expression module. Hub gene analysis and visualization of gene networks will be carried out using Cytoscape(5). Identification of these hub genes may reveal the key molecular drivers within treatment arms or relationships with clinical response.

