2.3.3 Gene pathway analysis

Following the identification of DEGs, gene modules of interest and hub genes, Gene Ontology and Pathway Analysis will be performed on each of these lists to establish which pathways are impacted in each comparison. The novel pathways for each arm comparison will guide our work towards specific mechanisms of action in COVID-19 patients. Mechanisms that vary between the arms of this study will also be identified by performing Gene Set Variation Analysis (GSVA)(6). This method generates a score for each pathway within the chosen pathway dataset, allowing for comparison of the pathways scores for each sample across the condition arms. This will be done using the linear modelling package limma. We will use the most recent release of pathway databases for this analysis, such as KEGG or Wikipathways.

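### WGCNA modules are related to clinical response and viral load by one-by-one correlations that do not adjust for entry severity or age, so a severity module can pass for a response module

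*Protocol*

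**What the plan says.** Section 2.2 assigns baseline control analysis by analysis:

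- Expression: "Differential gene expression analysis will control for baseline factors that may skew analysis by updating the statistic model design in DESeq2".
- Splicing: "Differential splicing analysis will be subject to weighting by multinomial covariate-balanced propensity scores to control for baseline confounding factors".
- Proteins: "Proteomics models will incorporate weighted baseline clinical data to avoid bias".

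It names no such control for WGCNA or GSVA.

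Section 2.3.2 correlates WGCNA modules with clinical traits and with treatment arm, and interprets the result: "Identification of these hub genes may reveal the key molecular drivers within treatment arms or relationships with clinical response". It lists no covariates.

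Section 2.3.3 fits GSVA pathway scores in limma, "allowing for comparison of the pathways scores for each sample across the condition arms". It lists no covariates and does not mention response.

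Section 2.5 takes viral load, serology, drug concentration and demographics together with baseline severity and says that all of these, including "clinical severity (baseline OSCI score) will be included in the pathway analysis model". Its next sentence describes the use: the factors are coded numerically and "input as clinical traits for analysis of correlation with eigengene values" of the WGCNA modules.

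**The concern.** An eigengene correlated separately with baseline OSCI, age, viral load and response gives a row of marginal correlations. None is conditional on another. Listing baseline severity as one more trait therefore does not remove its influence from the module-response correlation.

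This matters because response is not a randomised factor. Section 1 measures it as time to improvement or discharge. Section 1.1 admits patients from OSCI Grade 3, without oxygen, to Grade 5, on non-invasive ventilation or high-flow oxygen. Entry severity is a plausible common cause of blood expression and of time to discharge, and age is another. Section 2.2 accepts this reasoning for single genes, and a module eigengene summarises the same genes.

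At stake is interpretation. A module that mainly marks how ill patients were at entry could be put forward as related to drug response, and its hub genes as molecular drivers.

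**Working it through.** **The text.** The protocol gives no figure on this point to reproduce, so the first check is to set the sections side by side.

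| Analysis | Related to | Baseline control stated |
|---|---|---|
| DESeq2 (2.2, 2.3.1) | pre/post, response, arm | Yes, in the model design |
| Splicing (2.2, 2.3.4) | pre/post, arm | Yes, propensity weights |
| Proteins (2.2, 2.4) | arm, response | Promised in 2.2; the Mann-Whitney test that 2.4 thinks likely takes no covariates |
| WGCNA modules (2.3.2, 2.5) | arm, response, viral load and other traits | None; baseline factors are parallel traits |
| GSVA scores (2.3.3) | arm | Not listed in 2.3.3; 2.5 is ambiguous |

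The clear gap is the WGCNA row, for the non-randomised traits.

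**Sample size for the illustration.** Section 1.2.1.1 gives 286 samples sequenced and 14 removed: 286 − 14 = 272. There are three time points and four arms. If samples are spread evenly (an assumption), 272/3 = 90.7, about 91 per time point, and 272/12 = 22.7, about 23 per arm per time point.

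**Induced correlation.** Let severity correlate ρ with the module and ρ with response, with no direct link between those two. The marginal module-response correlation is then r = ρ × ρ. The protocol gives no ρ, so 0.3 to 0.5 is assumed.

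**How often it looks significant.** On Fisher's z scale, d = atanh(r) × √(n − 3). The probability of two-sided p < 0.05 is Φ(d − 1.96) + Φ(−d − 1.96), with √88 = 9.381 for n = 91 and √20 = 4.472 for n = 23. A simulation with 4,000 runs per setting tested the marginal correlation, and also the partial correlation given severity.

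| n | ρ | r = ρ² | d | Formula | Simulated, unadjusted | Simulated, adjusted |
|---|---|---|---|---|---|---|
| 91 | 0.3 | 0.09 | 0.847 | 13.5% | 12.9% | 4.7% |
| 91 | 0.4 | 0.16 | 1.514 | 32.8% | 32.8% | 4.5% |
| 91 | 0.5 | 0.25 | 2.396 | 66.9% | 67.5% | 5.2% |
| 23 | 0.3 | 0.09 | 0.404 | 6.9% | 7.0% | 4.9% |
| 23 | 0.4 | 0.16 | 0.722 | 11.2% | 11.9% | 4.8% |
| 23 | 0.5 | 0.25 | 1.142 | 20.8% | 21.3% | 4.9% |

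At ρ = 0.2 the unadjusted simulated rates are 7.0% (n = 91) and 5.6% (n = 23), so a weak dependence on severity does little harm.

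**Randomised arm.** The same simulation tested the module against a randomly assigned two-arm label. For ρ from 0.2 to 0.5 the rate stayed between 4.7% and 5.9%, with or without adjustment.

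**The case against.** The strongest reply is that 2.5 says in plain words that demographics and baseline OSCI go into the pathway analysis model. The linear model named for pathway scores is limma, which takes covariates, and the sentence on eigengene correlation is confined to WGCNA. For GSVA this stands: a reader might infer that the protocol refuses to adjust pathway scores, but the text is only ambiguous, and 2.3.3 relates those scores to arms, not to response. The reply does not rescue WGCNA, for which single-trait correlation is the stated method. Nor does the literal reading work as a covariate list. The same sentence includes viral load, which is sampled up to Day 29, and drug concentration, which 1.2.1.5 makes available only for patients given an experimental drug.

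A second tempting inference is that missing adjustment biases the arm comparisons. The documents do not support it. Arm is randomised, so only chance imbalance or selection into the RNA subset could produce a difference. Adjustment there adds precision.

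A third is that all pathway-level mechanisms come from unadjusted analyses while genes, splicing and proteins are all protected. That is also too strong. Section 2.3.3 runs pathway analysis on gene lists from the adjusted DESeq2 model, and the protein adjustment is itself doubtful.

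Two further points stand in part. WGCNA is exploratory and cautiously worded. And because baseline OSCI is among the traits, a severity module would show its severity correlation in the same output. This makes the confounder visible, but it does not say what remains of the response association once severity is accounted for.

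**Conclusion.** The point holds for WGCNA modules related to clinical response and viral load. As written, shared dependence on entry severity or age can make a module look related to either. It does not hold as a claim of bias in randomised arm comparisons. For GSVA it comes down to stating the covariates.

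Under assumed correlations of 0.3 to 0.5, the unadjusted rate of nominal significance is about 13% to 67% at n = 91 and 7% to 21% at n = 23, against about 5% after adjustment. The smaller size is the closer guide for analyses within one drug arm. These figures are an illustration and rest on four assumptions:

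- The values of ρ are not from the protocol. Restriction of OSCI to three grades at entry may make them smaller.
- Samples are spread evenly over arms and time points.
- The measured score captures severity fully. A three-level score may leave some confounding after adjustment.
- False positive here means significant although no link exists beyond severity. The marginal correlation itself would be real; the error lies in reading it as a link to response in its own right.

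The direction follows from the method. The size depends on ρ.

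**What to change.** - **2.3.2 and 2.5:** test module-response and module-viral-load associations in a linear model, for example limma on the eigengenes, with Day 1 covariates such as baseline OSCI, age and sex. Sections 2.2 and 2.3.1 do not itemise the covariates of the DESeq2 design, so the list should be written out once and shared. Present single-trait correlations as descriptive, and base hub-gene statements about response on the adjusted results.
- **2.3.3:** state that the limma arm model for GSVA scores uses the same Day 1 covariates, for precision.
- **2.5:** reword the claim of inclusion in the pathway analysis model. Separate Day 1 factors, which may be adjusters, from post-baseline viral load and drug concentration, which should not be adjusters in arm contrasts. Standard-of-care patients have no drug concentration.

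The cost is analysis wording and a few degrees of freedom, which count for more in models within one arm at about 23 patients than in pooled ones. Baseline OSCI, age and sex are already recorded, and limma is already planned for pathway scores.

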1.2.1.5 Pharmacokinetic drug concentration dataset

A pharmacokinetic dataset is available for each subject who received at least 1 dose of experimental drug and in whom drug levels were detectable. PK assessments were specific to the candidate agent and delivered by the pharmaceutical partners using validated assays for drug registration.

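### Section 2.5 enters drug concentration as a numeric trait in the masked, multi-arm WGCNA without restricting it to one drug, so a correlation can reflect the arm and the masking is undone

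*Protocol*

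**What the plan says.** Section 2.5 states: "Viral Load, SARS-CoV-2 Serology, Pharmacokinetic drug concentration, patient demographics and clinical severity (baseline OSCI score) will be included in the pathway analysis model". It continues: "These factors will be coded as numerical values and input as clinical traits for analysis of correlation with eigengene values of gene cluster modules". It gives no rule by drug, sampling day or unit, and none for patients without a PK value.

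The network in question covers several arms under masking. Section 2.3.2 says "we will assess whether any gene module is associated with one of the blinded treatment arms", and section 2.3 requires that "the groups will be blinded so that the bioinformatician will not know which patient group or SoC arm is which". The arm codes (A to D, for example) are to hold throughout the transcriptomic analysis.

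Section 1.2.1.5 says that PK assessments were specific to each agent, and that a PK dataset exists "for each subject who received at least 1 dose of experimental drug and in whom drug levels were detectable". Section 1.2 adds: "Each drug had slightly different pharmacokinetic (PK) sampling regimes and were mostly collected predose". Its table puts RNA on Days 1, 5 and 10 and gives each drug its own PK days. For tozorakimab the only post-baseline PK day is Day 15 ("Sample collected pre-dose and 15 minutes post-dose (Day 15").

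**The concern.** The project aims to identify mechanisms of action. A module that correlates with drug concentration would naturally be read as exposure-response, that is, as stronger evidence of mechanism than a difference between arms. That reading is sound only if the correlation is computed among patients on the same drug, with concentrations that can bear on the RNA sample. Section 2.5 requires neither. Across arms, the variation in a PK trait can come mostly from which drug a patient received, or whether any was given. The correlation then repeats the arm contrast, or reflects a difference in units.

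A second problem does not depend on how the trait is coded. PK data exist only in the drug arms and follow a different calendar for each drug. Giving them to the analyst during the masked stage discloses what section 2.3 says the analyst will not know.

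**Working it through.** The protocol states no sample size, alpha or power for this analysis, so there is no figure of its own to reproduce.

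**Step 1: PK days against RNA days (table in section 1.2)**

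| Drug | PK days | Same-day PK for post-treatment RNA (Days 5, 10) |
|---|---|---|
| Bemcentinib | 1, 4, 8, 15 | 0 of 2 |
| Tozorakimab | 1, 15 | 0 of 2 |
| Zilucoplan | 1, 5, 10, 15 | 2 of 2 |

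That is 2 of 6 post-treatment cells, both zilucoplan. All three drugs share Day 1 with RNA, but the Day 1 RNA sample precedes the first dose and so cannot reflect exposure. Day 15 PK comes after every RNA sample.

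**Step 2: what PK reveals about the arm**

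The three day patterns all differ, and SoC has no PK at all. A coded group with no PK is SoC. If sampling days come with the values, they separate the three drugs.

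**Step 3: what the correlation measures when there is no exposure-response**

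Assumptions, none from the protocol: one drug arm and SoC of equal size, SoC coded 0, log-normal PK with sigma 0.5 (median scaled to 1), eigengene SD 1, and a shift of d SD in the drug arm that is unrelated to concentration.

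- PK mean in treated patients: exp(0.125) = 1.133. Variance: (exp(0.25) − 1) × exp(0.25) = 0.365.
- Variance of the trait over both arms: 0.5 × 0.365 + 0.25 × 1.133² = 0.182 + 0.321 = 0.503. The share due to arm is 0.321 / 0.503 = 64%.
- Expected correlation: r = 0.25 × 1.133 × d / √(0.503 × (1 + d²/4)). This gives 0.19 at d = 0.5 and 0.30 at d = 0.8, although concentration has no effect.

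For the arm size, 272 usable samples over 3 days and 4 arms average 272 / 12 ≈ 23. The upper value of 35 is an assumption. Simulated share of Pearson tests significant at two-sided 0.05:

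| Patients per arm | d = 0.5 | d = 0.8 | Within the drug arm only |
|---|---|---|---|
| 23 | about 26% | about 56% | about 5% |
| 35 | about 39% | 74-76% | about 5% |

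**Step 4: other codings, 35 per arm**

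- A separate trait for each drug, all other arms coded 0, four arms: 59% at d = 0.5 and 92-93% at d = 0.8.
- Three drugs pooled on raw scales of 1:10:100, SoC missing, only the highest-scale drug shifting the module: about 50% and 87-88%.
- Same pooling on equal scales: about 5%.
- Four arms pooled on 1:10:100 with SoC coded 0 and all three drugs shifting the module: 13% and 24%.

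The pooled result thus depends heavily on scales that the protocol does not give.

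**The case against.** The strongest reply is that section 2.5 is a short statement whose details belong in a statistical analysis plan that may exist. A reader might infer that the three drugs are merged into one variable. The text does not say so: it speaks of traits in the plural, and one trait per drug fits equally well. That stands, but it does not remove the problem. A per-drug trait with the other arms coded 0 still largely indicates the arm (step 4), and the conflict with masking is the same. Treating patients on other arms as missing would avoid the false correlation, but the protocol does not say this.

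Other stronger readings also fail:

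- PK does not miss the RNA days altogether. Zilucoplan matches all three. Nor does WGCNA require same-day traits, since baseline OSCI is itself a patient-level value.
- Masking is not the only safeguard. Section 2.2 has baseline adjustment and propensity weighting, and section 2.6.5 has cross-validation. The licence to modify the analysis as results evolve is in section 2.3.1, on differential expression, not on WGCNA.
- Coding demographics numerically need not impose an order on ethnicity, because 0/1 indicators are numerical.
- The detectable-level condition describes, per subject, which data are available. It is not a rule to discard low exposures, and the number affected is unknown.

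It is also fair that the significant correlations in step 3 reflect a real drug effect on the module. The error lies only in reading them as exposure-response. Section 2.3.2 tests modules against arms separately, so a careful analyst could notice the overlap, but the plan does not ask for that comparison.

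**Conclusion.** The concern holds in limited form. Section 2.5 puts PK into a multi-arm network without confining it to one drug, while the protocol's own description of the data makes cross-arm PK values non-comparable or absent. With one drug plus SoC coded 0, a correlation with no exposure-response behind it is significant in roughly 26-39% of cases at an arm effect of 0.5 SD and 56-76% at 0.8 SD, against about 5% within one drug. These figures rest on assumed arm sizes, PK spread, zero coding and arm effects. They illustrate the mechanism and do not estimate what this dataset will show. No single figure can be given for pooling three drugs.

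The conflict with masking needs no such assumptions for SoC, which is recognisable by having no PK. For the individual drugs it holds if PK is supplied with its sampling days.

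**What to change.** Amend section 2.5 as follows:

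1. Remove PK concentration from the trait matrix of the masked multi-arm WGCNA. The other listed factors can stay.
2. Correlate PK with module eigengenes only within each drug arm, and release PK to the analyst only after the masked results are locked.
3. Use only PK samples that precede or coincide with the RNA sample, and do not treat Day 1 pre-dose values as exposure. For Day 5 and Day 10 RNA this leaves Days 4 and 8 for bemcentinib, the same-day samples for zilucoplan, and only the Day 1 sample taken 15 minutes post-dose for tozorakimab.
4. Where the records can be obtained, keep treated subjects with undetectable levels, as lowest rank or left-censored.

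Log or rank scale, change from baseline and the exact pairing of days are matters of preference and can be left to the analysts.

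The cost is some wording and code, plus a request for the undetectable-level records. Exposure-response for tozorakimab becomes explicitly limited, which the sampling schedule already implies.
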